## **Study Objective**

The objective of this study is to determine the safety, feasibility and efficacy of a bidirectional oxygenation PEEP mouthpiece in COVID-19 patients requiring supplemental oxygen.

## **Hypothesis:**

We hypothesize that the bidirectional oxygenation PEEP mouthpiece is a safe and effective respiratory therapy and will improve oxygenation, reduce the need for intubation, and improve survival in patients with COVID-19 and pulmonary compromise.

## **Background and Significance**

The COVID-19 virus is a rapidly spreading threat which is already placing a strain on healthcare systems across the world. Both public and private entities at all levels are attempting to develop diagnostic and therapeutic tools to diagnosis, treat, and limit its global impact. The basis of treatment is supportive care. These supportive measures, especially in patients with advanced pulmonary complications, are limited. Furthermore, treatments with non-invasive ventilation such as BIPAP and CPAP are contraindicated due to aerosolization of the virus.

Severe cases of COVID-19 often mimic the typical course of Adult Respiratory Distress Syndrome (ARDS) and its predictable sequelae. These patients often require intubation and ventilator support in order to sustain adequate oxygenation. Once a COVID-19 patient is intubated, Positive End Expiratory Pressure (PEEP) is a mainstay of treatment and is used in order to improve lung function, treat underlying atelectasis, improve oxygenation, and improve survival. In fact, early clinical data as well as reports from front line physicians treating COVID-19 suggest that PEEP has been the **MOST EFFECTIVE** treatment modality. In many cases, PEEP has resulted in improved oxygenation and improved survival.

PEEP decreases the propensity for the alveoli to collapse by increasing the air pressure in the lungs. This residual pressure in the lungs at the end of exhalation decreases shunting and allows for more complete gas exchange and improved oxygenation. In patients, PEEP is one of the safest ways to increase  $\text{PaO}_2$  and is used on almost all modern ventilator settings.

We have developed a simple, comfortable, and straightforward mouthpiece with a bidirectional valve that effectively delivers PEEP with every breath (GO2 PEEP MOUTHPIECE, image 1). The GO2 device is a 60% TPS (thermoplastic styrene-internal component)/30% PP (polypropylene-rigid external component)/10% silicone (external valve component) mouthpiece.

### Image 1. GO2 PEEP MOUTHPIECE

1a – PEEP Mouthpiece valve closed during expiration.

1b – PEEP Mouthpiece valve open during inhalation.

Initial testing using the bidirectional oxygenation mouthpiece on healthy subjects has been encouraging. Crouse et al. studied nine subjects during exercise and reported that the “Wearable Positive End-Expiratory Pressure Valve Increases Aerobic Capacity and Performance.” Subjects were assigned at random to the novel bidirectional oxygenation mouthpiece, a standard oxygenation mouthpiece, or nothing at all. Subjects wearing the bidirectional oxygenation mouthpiece showed an improvement in VO2 max of 6.1% compared to the standard mouthpiece and 4.0% compared to no mouthpiece. The endurance test showed an improvement of 6.5% compared to the standard mouthpiece and 6.0% compared to no mouthpiece. All results had p-values < 0.05. No adverse events were reported during the testing. Furthermore, the consumer version of this device, which is being used by athletes during vigorous exercise, has sold over 10,000 units to date with no reported adverse events.

Prior to the current pandemic, we planned to compare the GO2 PEEP MOUTHPIECE to incentive spirometry in cardiac surgical patients. We submitted our protocol for a randomized pilot study in postoperative heart surgery patients to the Emory IRB several months ago and it was recently approved. We were gearing up to start our clinical trial at Emory when the pandemic hit. Our study enrollment, like most clinical trials at Emory, is currently temporarily suspended.

We believe that early application of the GO2 PEEP MOUTHPIECE in non-intubated COVID-19 patients may improve outcomes and save lives. Furthermore, this device may allow for less strain on limited resources, especially ventilators. This PEEP mouthpiece could be employed in conjunction with oxygen therapy to improve oxygenation and avoid intubation.

### **Requirements**

We are seeking a rapid evaluation of the safety, efficacy, and feasibility of the device in patients with COVID-19 and pulmonary compromise. In order to test the performance of the device, we would identify a cohort of patients with a diagnosis of COVID-19. This cohort would be

characterized as those who require supportive care with supplemental oxygen but for whom ventilator support is not yet indicated or available. Once the patient is identified, consents to the study, and progresses to meet inclusion criteria based on oxygen requirements (>6L NC), then baseline measurements of oxygen saturation, respiratory rate, heart rate, blood pressure and blood gas results (when available) would be recorded. Furthermore, perceived effort of respiration would be measured including stridor, grunting, nasal flaring, or accessory muscle use. Patients would then be given the GO2 PEEP MOUTHPIECE for use in conjunction with oxygen therapy. Metrics would be recorded prior to initiation of therapy, 5, 10 and 15 minutes after GO2 PEEP therapy and 15 minutes after cessation of therapy.

### **Safety**

This design allows for rapid analysis in a safe manner. The brief and limited application of the GO2 PEEP MOUTHPIECE will limit patient exposure if the device is determined to be non-efficacious. The level of pressure generated by our device is 10 cm H2O. This is safe when compared to the safe levels of PEEP generated by the ventilator, typically in the range of 5-10 cm/H2O. Furthermore, we are well below maximal PEEP levels of up to 30 cm/H2O, which is often required in severe cases or when positive pressure ventilation mode is required.

### **Deliverables and Timing**

This would serve as a limited safety and feasibility study to determine if further investigation is necessary. We estimate evaluation in 5 patients could be reached within one week. Thereafter, a more formal analysis could be performed as necessary.

### **Research Design and Methods**

#### *Design*

This study will utilize a single center, single arm, pilot study design.

#### *Target Study Population*

COVID-19 positive patients with pulmonary compromise requiring supplemental oxygen.

#### *Inclusion Criteria*

- 1) COVID-19 positive
- 2) Oxygen saturation  $\leq 92\%$
- 3) Able to provide informed consent
- 4) Receiving oxygen  $\geq 6\text{L}$  nasal cannula
- 5) Not currently requiring intubation

#### *Exclusion Criteria*

- 1) Unable or unwilling to provide informed consent

- 2) Cognitive impairment
- 3) Rapidly decompensating status requiring urgent or emergent higher level of care

### **Study Endpoints**

#### *Primary Endpoint*

Improved oxygen saturation by pulse oximetry after treatment with the GO2 PEEP MOUTHPIECE.

The secondary endpoints include:

1. Respiratory rate
2. Heart rate
3. Blood pressure
4. Subjective work of breathing
5. Arterial blood gases (if available)

Both primary and secondary endpoints will be used to evaluate the safety as well as the efficacy of the GO2 PEEP MOUTHPIECE.

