### **Study Procedures**

After an eligible COVID-19 patient on supplemental oxygen has been identified, the research coordinator will contact patient via HIPPA compliant communication technology. The study will be verbally explained in detail with the patient. At time of verbal consent, instruction on use of the device will be performed by research team. If the patient progresses to meet the inclusion criteria and is enrolled in the trial, baseline metrics as above will be recorded. Patients will be provided a GO2 mouthpiece to be used in conjunction with and oxygen delivery face mask set to deliver an equivalent FIO2 to their previous therapy. **All patients will be instructed to breathe slowly and deeply through the mouthpiece for 15 minutes total.** Metrics for primary and secondary endpoints will be recorded before and after use of the mouthpiece (immediately prior to use and then at 5, 10 and 15 minutes of use and then 15 minutes after cessation of use).

Any decline in patient condition will result in immediate removal of the GO2 PEEP MOUTHPIECE and further appropriate care by the critical care team.

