## Statistical Analysis Plan

As an emergent COVID-19 study, our goal is to examine the safety, feasibility and efficacy of adding the GO2 PEEP MOUTHPIECE to COVID-19 patients already on oxygen therapy.

We will assess safety, feasibility and efficacy by observation of changes in the primary and secondary endpoints. At the conclusion of the study, we will assess metrics before and after application of the GO2 PEEP MOUTHPIECE, but given the few number of patients and low power of this initial study, statistical significance is not the focus of the analysis. However, we plan to provide statistical summaries that would be useful in a possible subsequent study, such as overall efficacy of the device and patterns and trends in primary and secondary endpoints.

Summary statistics on oxygen saturation (primary endpoint) and respiratory rate, heart rate, blood pressure, subjective work of breathing, and arterial blood gases as available (secondary endpoints) will be reported at each measurement occasion for each patient.

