### *Subject Safety*

Subject safety is of utmost importance throughout this study. If at any time there is a worsening of the patient's condition, the GO-2 PEEP MOUTHPIECE will be immediately removed and standard therapy will be directed by the critical care medicine team.

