## **Data Safety Monitoring Plan**

With this very small, single-center, open label trial, there will not be a DSMB. However, the Principal Investigator will personally monitor each patient's use of the device. Therefore, there will be one-on-one physician monitoring, assessment and documentation for adverse effects and intolerance of device usage. If the subject experiences an adverse event as a result of the device, and the investigator staff believe it is in the best interest to discontinue study participation, the patient will be withdrawn. Any unanticipated or unforeseen complications will be reported by the investigator (or authorized designee) to the IRB.

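### Does the primary endpoint need a single named SpO2 reading and a written rule for patients whose mouthpiece comes off early?

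*Combined protocol and SAP*

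**What the plan says.** Under Primary Endpoint the protocol gives a direction and no time: "Improved oxygen saturation by pulse oximetry after treatment with the GO2 PEEP MOUTHPIECE". Study Procedures sets the readings "immediately prior to use and then at 5, 10 and 15 minutes of use and then 15 minutes after cessation of use", which makes one baseline and four later values, three on the device and one off it. The Schedule of Assessments has the same five columns, and it places blood gases only at baseline and at the 15-minute column before cessation.

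The Statistical Analysis Plan says "We will assess safety, feasibility and efficacy by observation of changes in the primary and secondary endpoints". It also offers summaries for a possible later study, among them "overall efficacy of the device and patterns and trends in primary and secondary endpoints", and commits that summary statistics on SpO2 and the secondary measures "will be reported at each measurement occasion for each patient". It states that power is low and that significance is not the aim.

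On early removal, Study Procedures says "Any decline in patient condition will result in immediate removal of the GO2 PEEP MOUTHPIECE", and Subject Safety agrees: "If at any time there is a worsening of the patient's condition, the GO-2 PEEP MOUTHPIECE will be immediately removed". The Data Safety Monitoring Plan adds that, after a device-related adverse event, if "the investigator staff believe it is in the best interest to discontinue study participation, the patient will be withdrawn". None of the three says what happens to that patient's readings in the analysis.

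**The concern.** A primary endpoint should fix the measurement, the time and the summary before data are seen. Here the time is open, and the candidates answer different questions: the 15-minute reading shows what happens on the device, and the reading 15 minutes after cessation shows what persists. If the team picked whichever looked best, the efficacy statement would lean towards the device even if it did nothing.

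Early removal could lean the same way. Decreased saturation is on the adverse-event list, so removal may be driven by the primary variable itself. A 15-minute mean over only those still wearing the mouthpiece would then drop the worst patient, who is one fifth of the data. The Deliverables and Timing section says the study is to show whether further investigation is needed, so a flattering headline could matter.

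**Working it through.** **Inputs from the documents.** Five patients in a single arm (Sample Size and Accrual). Readings at 0, 5, 10 and 15 minutes and at 15 + 15 = 30 minutes. No SpO2 variability, alpha, power or success threshold is given, so there is no stated figure to reproduce.

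**Assumptions.** Normal readings with constant SD, no device effect, and correlation r per 5 minutes decaying with time, with r from 0 to 0.95.

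**1. Choosing the reading afterwards.** At r = 0 the answer is exact. The best of four post-baseline means fails to beat baseline only if baseline is the largest of five exchangeable means: 1 - 1/5 = 0.80. For a choice between 15 minutes of use and 15 minutes after cessation it is 1 - 1/3 = 0.667. Simulation gives the rest:

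| r | Best of 4: P(mean change > 0) | Mean gain (reading SDs) | Best of 2: P(mean change > 0) | Mean gain (reading SDs) |
|---|---|---|---|---|
| 0 | 0.800 | 0.46 | 0.667 | 0.25 |
| 0.5 | 0.792 | 0.40 | 0.662 | 0.24 |
| 0.8 | 0.776 | 0.29 | 0.645 | 0.18 |
| 0.9 | 0.766 | 0.22 | 0.636 | 0.13 |
| 0.95 | 0.760 | 0.16 | 0.631 | 0.095 |

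A fixed reading gives 0.50 and 0. If correlations between the change scores are varied directly from 0 to 0.95, best-of-four runs from 94% down to 59%, so the size depends on the model, though the direction does not.

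**2. Leaving out a removed patient.** In a sample of five the expected lowest and second-lowest values are -1.163 and -0.495 SD. Dropping the lowest shifts the mean by 1.163/4 = 0.291 SDs of change. Dropping the two lowest shifts it by (1.163 + 0.495)/3 = 0.553. These are upper limits. If removal is unrelated to SpO2, the shift is 0. If the patient lowest at 5 or 10 minutes is dropped (r from 0 to 0.9), the shift is +0.14 to +0.23.

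**3. Does the obvious rule repair this?** With no trend, carrying the last on-device reading forward gives -0.01 to -0.12 SDs of change, which looks safe. Now suppose the removed patient would have fallen a further 1 SD of change by 15 minutes. The true five-patient mean is then lower by 1/5 = 0.20 SD, and the rule's error becomes 0.20 - 0.12 = 0.08 at one end and 0.20 - 0.01 = 0.19 at the other, both in the device's favour. The sign depends on whether a patient taken off for worsening would have gone on worsening, and the documents cannot settle that.

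**4. Does the plan contain the rules that cause the harm?** Parts 1 and 2 measure a best-reading choice and a completers-only mean. Neither is in the plan. As written, it yields 5 patients x 5 readings = 25 saturation values, fewer if readings are missed. From these, all 5 x 4 = 20 changes, their means and their SDs can be computed by hand, and a blank cell after removal is visible.

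**5. What would a named contrast deliver?** Its 95% interval has half-width t(0.975, 4)/sqrt(5) = 2.776/2.236 = 1.24 SDs of change. The SD is known only to between 0.60 and 2.87 times its estimate, from sqrt(4/chi-square) at the two limits. Such an interval rarely settles a question of efficacy, whichever reading is used.

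**The case for a change.** The strongest case for a change is that a listing lets a reader detect selection but does not stop the authors from writing a selective headline, and that with five patients one exclusion moves the result a long way. For example, if four patients gain 2 points and one is removed at -6, the mean is +2.0 without that patient and (4 x 2 - 6)/5 = +0.4 with that value kept. The remedy would be wording only, and a paired SD at a named time is useful for sizing a later trial.

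Part of this stands. The gaps are real, and the efficacy statement is undefined. The rest is weaker. The paired SD comes straight from the listed values. The example works only if a reader is not shown the fifth patient, and the plan reports each patient. Device removal does not in itself end data collection, and study data come from the medical record. Naming one reading would also not make the headline neutral. Entry requires saturation of 92% or below, and patients move to a face mask and are told to breathe slowly and deeply. If the qualifying value also served as baseline (assumed), a fixed 15-minute reading with no device effect would show a positive mean in about 60-94% of studies, under correlations of 0 to 0.9 and a cut-off 0 to 1 SD above the patient's own level. A descriptive profile over time is a fair choice for a study that looks for patterns and trends.

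The schedule's use of the word after for readings taken during use is a clerical matter. Study Procedures says they are taken during use, and the table has a separate post-cessation column.

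**Conclusion.** No change is called for. The plan leaves a definition and a handling rule unwritten, in a five-patient descriptive pilot that reports every reading for each patient and attaches no test or threshold to any of them. Analysts would fill the gap sensibly by showing all four changes, with the 15-minute on-device value as the natural one to describe first (blood gases are timed there too), and by listing any removed patient with the readings taken.

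The conditional sizes are 76-80% against 50% for a favourable mean, and up to 0.29 SDs of change for one omitted patient. Both need a choice that the plan does not make and that its listing would expose. They also rest on assumed correlations, because the documents give no SpO2 variability. The early-removal rule that comes first to mind can err in either direction, so writing it in brings no clear gain. The judgement would differ if the study carried a success criterion or reported only group means.

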## Schedule of Assessments

Study Procedures	Prior to treatment with the mouthpiece	5 mins after PEEP therapy	10 mins after PEEP therapy	15 mins after PEEP therapy	15 minutes of after cessation of PEEP therapy
Consent	X				
Oxygen saturation	X	X	X	X	X
Respiratory rate	X	X	X	X	X
Heart rate	X	X	X	X	X
Blood pressure	X	X	X	X	X
Work of breathing 	X	X	X	X	X
Arterial blood gases (if available)	X			X	
Adverse events	X	X	X	X	X

 presence of any of the following: stridor, grunting, nasal flaring, or accessory muscle use

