## Sample Size and Accrual

The sample size for this emergent study will be 5 patients admitted with laboratory proven COVID-19 and pulmonary compromise. This number will be sufficient to demonstrate the safety, feasibility and possible efficacy of the GO2 PEEP MOUTHPIECE in improving oxygenation.

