#### *Adverse Events*

Patients will be assessed for the following adverse events:

- Decreased oxygen saturation
- Increased respiratory rate
- Increased heart rate
- Low blood pressure
- Increased work of breathing
- Worsening arterial blood gases (if available)
- Patient unable to tolerate the mouthpiece

All serious adverse events will be assessed and reported per the Emory IRB Policies and Procedures.

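### The only CO2 measure is an optional blood gas, yet the plan's safety conclusion covers all five patients whether or not they have one

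*Combined protocol and SAP*

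**What the plan says.** The primary endpoint is "Improved oxygen saturation by pulse oximetry after treatment with the GO2 PEEP MOUTHPIECE", with no minimum gain. The secondary endpoints are respiratory rate, heart rate, blood pressure, subjective work of breathing and arterial blood gases if available. Study Endpoints then adds that "Both primary and secondary endpoints will be used to evaluate the safety as well as the efficacy of the GO2 PEEP MOUTHPIECE".

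The blood gas is conditional wherever it appears:

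- Requirements: at baseline, "blood gas results (when available) would be recorded".
- Schedule of Assessments: before use and at the 15-minute point, if available.
- Adverse Events: worsening gases are listed, if available, with PaCO2 and pH not named.
- Statistical Analysis Plan: "arterial blood gases as available (secondary endpoints) will be reported at each measurement occasion for each patient".

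No other CO2 measure (end-tidal, transcutaneous or venous) is planned.

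Patients stay on oxygen through a face mask at an FIO2 equivalent to their previous therapy. Study Procedures says "All patients will be instructed to breathe slowly and deeply through the mouthpiece for 15 minutes total". Adverse Events counts a rise in respiratory rate but not a fall. Work of breathing is the presence of any of four signs of increased effort. The Data Safety Monitoring Plan adds one-on-one physician monitoring. Of the five patients, Sample Size and Accrual says: "This number will be sufficient to demonstrate the safety, feasibility and possible efficacy of the GO2 PEEP MOUTHPIECE in improving oxygenation".

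**The concern.** One hazard a reader would want a safety conclusion to cover is reduced ventilation with a rise in PaCO2. A patient whose oxygenation improves with ventilation unchanged, and one whose oxygenation improves while CO2 rises, differ in PaCO2 and pH but may look alike on the other recorded measures.

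- Saturation on enriched oxygen responds little to PaCO2, and any oxygenation gain from PEEP pushes it the other way.
- Respiratory rate is partly set by the breathing instruction, and only an increase is an adverse event.
- Heart rate, blood pressure, effort and visible distress may give indirect warning but do not measure ventilation.

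The safety statements in Study Endpoints and in Sample Size and Accrual do not depend on how many patients have two gases. With none, the text would still support the same claim. Deliverables and Timing says the result is meant to show whether further investigation is needed, so an over-wide claim would carry forward.

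**Working it through.** The plan gives no figure to reproduce: five patients are stated without alpha, power, effect size or standard deviation. Two illustrations follow.

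**1. How far saturation moves when PaCO2 rises.**

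From the documents: saturation at entry is at most 92%, and patients are on supplemental oxygen. Assumed, because the documents do not give them: FIO2 0.40 to 0.60, starting saturation 91% at PaCO2 40 mmHg, haemoglobin 13 g/dL, arteriovenous oxygen difference 4.5 mL/dL, respiratory quotient 0.8, and a pH fall of 0.008 per mmHg of CO2.

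Formulas:
- Alveolar PO2 = FIO2 × 713 − PaCO2/0.8
- Oxygen content = 1.34 × 13 × saturation + 0.003 × PO2
- Arterial content = end-capillary content − q/(1 − q) × 4.5, where q is the shunt fraction
- Saturation from the Severinghaus curve with a pH shift: S = 1/(23400/(v³ + 150v) + 1), with v = PO2 × 10^(0.48 × (pH − 7.4))

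Worked case, FIO2 0.40:
- Alveolar PO2 is 285.2 − 50 = 235.2 mmHg at PaCO2 40, and 285.2 − 75 = 210.2 mmHg at PaCO2 60.
- End-capillary content goes from 18.09 to 17.98 mL/dL.
- The shunt that gives 91% at the start is q = 0.314, so the shunt term is 0.314/0.686 × 4.5 = 2.06.
- Arterial content goes from 16.04 to 15.92 mL/dL and pH from 7.40 to 7.24. Saturation goes from 91.00% to 90.16%.
- With q = 0.284 the shunt term is 1.78, arterial content is 16.19 mL/dL, and saturation is 91.66%.

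| FIO2 | q | PaCO2 40 | PaCO2 50 | PaCO2 60 | PaCO2 60, shunt 3 points lower |
|---|---|---|---|---|---|
| 0.40 | 0.31 | 91.00 | 90.61 | 90.16 | 91.66 |
| 0.50 | 0.34 | 91.00 | 90.66 | 90.30 | 91.91 |
| 0.60 | 0.36 | 91.00 | 90.68 | 90.35 | 92.06 |

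The fall is 0.32 to 0.39 point at PaCO2 50 and 0.65 to 0.84 point at PaCO2 60. With the smaller shunt, saturation at PaCO2 60 is 0.66 to 1.06 points above the start. Starting values from 88% to 92% give a fall of about 0.6 to 0.8 point and, with the smaller shunt, a net rise of about 0.6 to 1.4 points. A 2-point shunt reduction also gives a net rise. On room air the same model falls from 91% to about 84.5%, so the masking comes from the enriched oxygen.

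**2. What the number of paired gases decides.**

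Let p be an assumed true rate of CO2 retention and a the assumed share of patients with paired gases. The chance that paired gases show at least one case in five patients is 1 − (1 − p × a)^5. For p = 0.2:
- a = 1: 1 − 0.8^5 = 67%
- a = 0.5: 1 − 0.9^5 = 41%
- a = 0: 0%

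If no case is seen among k patients with paired gases, the one-sided 95% upper limit on the rate is 1 − 0.05^(1/k): 45% for k = 5, 78% for k = 2 and 95% for k = 1. With k = 0 there is no information.

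**The case against.** A reader might infer that safety is judged from oximetry and vital signs alone. The documents do not support that. Work of breathing and blood gases are endpoints, gases are scheduled at two time points, worsening gases and intolerance are adverse events, a physician monitors each patient, and the device comes off on any decline. Where both gases exist, CO2 retention can be seen. The other measures may miss it; it is too strong to say they can never hint at it.

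A reader might also infer that the session is likely to cause under-ventilation. The instruction is to breathe slowly and deeply, and depth protects ventilation. With an assumed dead space of 180 mL, 400 mL × 24/min gives (400 − 180) × 24 = 5.3 L/min of alveolar ventilation, and 600 mL × 16/min gives (600 − 180) × 16 = 6.7 L/min, at the same minute volume of 9.6 L/min. PaCO2 of 60 rather than 40 needs a sustained one-third loss of alveolar ventilation (40/60 at constant CO2 production). Nothing in the documents points to that in 15 observed minutes. What stands against the plan is narrower: the instruction makes respiratory rate hard to interpret.

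It is also fair that the plan has no rule classing a patient as safe, disclaims statistical significance, calls itself a limited pilot, and will list available gases per patient, so a careful reader could count the pairs. But that listing does not limit the safety claim. Finally, the proposed change detects no additional case. It corrects what is claimed, which is its purpose.

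**Conclusion.** The point holds as a limit on what the trial can conclude. CO2 is measured only by an optional gas, and for a patient without both gases the remaining measures do not measure ventilation and may miss CO2 retention. The modelled loss of saturation at PaCO2 60 is under 1 point, and a modest fall in shunt can make it a net gain, which would meet a primary endpoint that sets no minimum gain. These figures rest on an assumed shunt model, FIO2 and starting values. They show insensitivity of saturation, not the likelihood of retention. The short, observed exposure limits harm but does not put CO2 data into the conclusion. Even complete gases in five patients with no case would leave an upper limit of 45%. The change should be made, but the point does not undermine the study.

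**What to change.** Revise Study Endpoints, Statistical Analysis Plan, and Sample Size and Accrual as follows:

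- For all patients, limit the safety conclusion to oxygenation, haemodynamics, work of breathing and tolerance.
- Assess ventilation only in patients with both a pre-use and a 15-minute gas. Report how many have both, and each such patient's change in PaCO2 and pH.
- State that no conclusion on CO2 retention is drawn for the other patients, and that unchanged or higher saturation is not evidence of preserved ventilation.
- Reword the claim in Sample Size and Accrual that five patients suffice to demonstrate safety, so that it matches these limits.

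This takes a few sentences and requires no added blood gas. The cost is a narrower safety claim, possibly with no ventilation data at all if no patient has both gases.
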